9.1.3 Trial operating characteristics

Simulations to assess the operating characteristics of the pilot study were performed. The simulations aimed at using the best data currently available to estimate the likely outcomes in the pilot study.

As a basis for the simulations, a dataset of 4,288 women aged 40-74 sampled from the Karma Cohort was used. Each woman had Stratus measured density from two mammograms taken at two different points in time (approximately two years in between the two time points as this is the screening interval in the Swedish national screening program). Summary statistics of the density at the two timepoints:

Time point 1: 25.5% (mean), 18.9% (median), IQR 8.3-35.2, 0.1 (min), 99.2 (max)

Time point 2: 23.3% (mean), 18.7% (median), IQR 8.3-34.4, 0.1 (min), 99.8 (max)

Women with BI-RADS categories B, C, and D will be invited to the Karma CREME-1 study. All women with a BI-RADS A density, which corresponds to women with a STRATUS density measures of 2% or lower ($n=240$), were removed from the dataset. The remaining women were used for simulations.

The following assumptions were used for all simulations:

- Age: 40-74
- BI-RADS: B, C, and D
- The density for women in the control arm is only affected by the natural reduction in density that typically comes with increased age. For simulations under the null, this applied also to the treatment arms
- 65% of the women in the treatment arm are good compliers and are assumed to get the whole density reduction that topical application of endoxifen can induce.
- 25% of the women in the treatment arm are poor compliers and are assumed to get half of the density reduction that topical application of endoxifen can induce.
- 10% of the women in each arm drop out of the study. It was assumed that the probability of dropout is proportional to the density reduction a given woman gets from the treatment (this is consistent with previous data that shows that it primarily is women who get a density reduction of tamoxifen who also experience side effects).
- The density reduction that topical application of endoxifen induces is proportional to each woman's density at baseline.
- Comparison between treatment and control arm will be done using a Wilcoxon test in the full phase II trial using a two-sided alpha=0.05 to declare statistical significance.

The assumption about the effect size (anticipated density reduction by using topical endoxifen) was then varied in different simulations according to the following:

- No or very little density reduction by using topical endoxifen (null hypothesis):

- 0% density reduction
- 1% density reduction
- 2% density reduction
- A clinically meaningful density reduction (alternative hypothesis):
 - Best guess. The density reduction by using topical application of endoxifen was assumed to the reduction seen in the pilot study of the Karisma-1 (oral tamoxifen, 10 and 20 mg) trial, i.e. 12% of the baseline density (range 1-19%).
 - Slightly smaller effect size than our best guess. Assuming the density reduction to be 10%
 - Slightly larger effect size than our best guess. Assuming the density reduction to be 14%

Given the dataset from the Karma Cohort and the assumptions listed above, the likely results from the pilot trial were simulated. Briefly, a trial cohort of 3x30 women by drawing women from the Karma Cohort and applying the density reduction in the treatment arm according to the assumptions above was repeatedly ($N_{sim}=1000$) simulated. Based on the results from the pilot trial, a decision on how to perform a larger, adequately powered study will be taken. Since the pilot study is not designed to show statistically significant results in terms of differences in density reductions between the three trial arms, a simple criterion based on the differences in mean density reductions between the placebo and treatment arms will be used for deciding about performing a larger trial. Whatever criterion picked, there will be non-zero probabilities of the pilot leading to false negative or false positive results. **Tables 4 and 5** summarize these probabilities for different choices of criteria.

Table 4. The table shows the probabilities of the pilot trial showing a false negative result based on different criteria for declaring a positive result from the pilot study. Simulations performed under the alternative hypothesis of a clinically meaningful reduction in density induced by topical application of endoxifen.

Criterion	Density Reduction		
	10%	12%	14%
mt-mc > 0%	10%	7%	3%
mt-mc > 1%	27%	20%	16%
mt-mc > 2%	52%	43%	33%
mt-mc > 3%	74%	66%	59%

Table 5. The table shows the probabilities of the pilot trial showing a *false positive* result based on different criteria for declaring a positive result from the pilot study. Simulations performed under the null hypothesis of no or only a very small reduction in density induced by topical application of endoxifen

Criterion	Density Reduction		
	10%	12%	14%
mt-mc > 0%	50%	56%	57%
mt-mc > 1%	24%	33%	35%
mt-mc > 2%	8%	16%	17%
mt-mc > 3%	2%	5%	5%

Based on these simulations of the operating characteristics of the trial, the criterion $mt-mc > 0\%$ as a criterion for a positive result from the pilot trial and for moving forward with a larger trial with adequate power for showing a statistically significant density reduction from topical endoxifen will be used.

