Healthy post-menopausal women participating in mammographic screening program at SöS Bröstcentrum with a measurable mammographic density, i.e., $\geq 4.5\%$ density (volumetric) measured by Volpara. No history of coagulopathies, cardio-vascular disorders and cancer.

Duration of treatment

6 months

Duration of participants involvement in the study

6 months of exposure to active compound or placebo

Efficacy assessments

Mammographic density after 3 and 6 months.

Safety assessments

The safety profile of each individual and dose group will be determined by clinical assessment, laboratory findings and participant reports. Laboratory findings and AEs will be followed throughout the study period. A Data and Safety Monitoring Board will provide safety oversight of the study.

Statistical methods

Karma CREME-1, is a pilot study conducted to aid the design of a larger future trial. As such, the pilot study is not powered to show statistical significant reductions in breast density in the treatment arms compared to the control arm. Rather, results of the pilot study will be qualitatively presented and assessed, which will aid in making decisions about dosing, study length, and sample size for the larger trial.

Efficacy: Assess change in mammographic density from baseline to 3 and 6 months and from 3 to 6 months of study drug administration.

Tolerability: Assess the grade, severity and frequency of side effects

Safety: rank adverse events by severity, grade, interventions, and resolution.

Table of Contents

PROTOCOL REVISION HISTORY	2
PROTOCOL SYNOPSIS	3
1 LIST OF ABBREVIATIONS AND DEFINITION OF TERMS	8
2 ETHICS	9
2.1 ETHICAL AND REGULATORY REVIEW	9
2.2 ETHICAL CONDUCT OF THE STUDY	9
2.3 PARTICIPANT INFORMATION AND CONSENT	9
2.4 PARTICIPANT DATA PROTECTION	9
3 ADMINISTRATIVE STRUCTURE	10
4 INTRODUCTION	11
5 STUDY RATIONALE	11
5.1 BACKGROUND	11
5.2 TOPICAL ADMINISTRATION RATIONALE	12
5.3 ENDOXIFEN RATIONALE	12
5.3.1 TOPICAL ENDOXIFEN - PHASE 1 DATA	12
5.3.2 PLASMA ENDOXIFEN LEVELS AFTER EXPOSURE TO ORAL TAMOXIFEN	12
5.4 DOSING RATIONALE	13
5.5 MAMMOGRAPHIC DENSITY	13
5.6 STUDY DURATION	14
5.7 CONCLUSION	15
6 BENEFIT-HARM ASSESSMENT	15
6.1 BACKGROUND	15
6.2 SAFETY	16
6.2.1 RISK MITIGATION STRATEGY -SAFETY	16
6.3 TOLERABILITY	16
6.3.1 LOCAL SIDE EFFECTS	16
6.3.2 SYSTEMIC SIDE EFFECTS	17
6.4 BENEFIT-HARM ASSESSMENT OF FREQUENT MAMMOGRAMS	18
6.5 POSSIBLE BENEFITS OF PARTICIPATION IN THE TRIAL	19

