8 STUDY OBJECTIVES AND ENDPOINTS

8.1 Primary objective: Breast Density Reduction

- Primary objective is to determine the effect size of the breast density change between topical placebo and two doses of topical endoxifen. The effect size will permit sample size calculations for statistical significance in a future phase III trial.

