8.1.1 Primary endpoint

- Primary endpoint is to determine change, on an individual level, in mammographic breast density, measured at 3 and 6 months after study entry (=baseline screening-mammography).

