9.1.2 Analysis of the primary endpoint (effectiveness)

The analysis of the primary endpoint qualitatively and quantitatively summarize difference in density change between baseline and at 3 and 6 months follow-up between the three arms. More specifically, the difference in density between baseline and at 3 and 6 months follow-up, respectively, for women in the placebo arm (ΔD_p) and in the two endoxifen arms (ΔD_{e1} and ΔD_{e2}), will be computed. Subsequently, the difference between ΔD_p and ΔD_{e1} as well as ΔD_p and ΔD_{e2} (at both 3 and 6 months) will be assessed.

The primary analysis will be performed on an intention to treat (ITT) basis, and a per protocol (PP) analysis will be performed as a secondary analysis. Women who stop using topical endoxifen will be encouraged to remain in the study and come in for an exit mammography. The density measured in these mammograms will be used in the analyses of the ITT population. Our experience from the Karisma-2 study is that virtually all women accept an exit mammography if choosing to withdraw from the study. However, women who drop out of the study and do not come in for additional

mammography appointments will be assumed to not have any density reduction for the ITT analysis. Sensitivity analyses where density for women who drop out is imputed based on age and density at baseline will also be performed.

Since this is a pilot study, which is not powered for showing statistical significance when testing for differences in mammographic density reduction between the treatment arms and the control arm, a simple criterion based on the difference in the mean of the density reduction across the two treatment arms and the density reduction in the control arm will be used instead. The concept mt is defined as the mean of the reduction in mammographic density across all women in the two treatment arms ($n=60$) and the mc to be the mean on the reduction in mammographic density in the control arm ($n=30$). The result of the trial as mt minus mc will be summarized.

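### Does the pilot's go rule (mt-mc > 0%) fail because it names no visit, and its effect size because no confidence interval is named?

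*Combined protocol and SAP*

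**What the plan says.** The primary endpoint (8.1.1) is individual change in mammographic density "measured at 3 and 6 months after study entry", with neither visit ranked above the other. Section 9.1.2 computes "the difference in density between baseline and at 3 and 6 months follow-up, respectively", for each arm, and compares each dose with placebo at both visits. It then defines mt over the 60 women on either dose and mc over the 30 on placebo, and adds: "The result of the trial as mt minus mc will be summarized". No visit is attached to mt or mc. The synopsis lists a further contrast: "Assess change in mammographic density from baseline to 3 and 6 months and from 3 to 6 months of study drug administration".

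Section 9.1.3 says that "a simple criterion based on the differences in mean density reductions between the placebo and treatment arms will be used for deciding" about a larger trial, and settles on mt-mc > 0% "as a criterion for a positive result from the pilot trial and for moving forward with a larger trial with adequate power". Section 8.1 gives the purpose of the estimate: "The effect size will permit sample size calculations for statistical significance in a future phase III trial". The descriptive statistics named in 9.1.1 are n, mean, SD, interquartile range, median, minimum and maximum. No confidence interval appears.

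Three other statements bear on the point:

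- Section 9.1 places the detailed analysis in a separate SAP, in final draft before study start and approved before database lock. Its text is not in the combined document.
- The synopsis and section 9 describe an unpowered pilot with qualitative results that inform dosing, study length and sample size.
- On drop-outs, 9.1.2 says of exit mammograms: "The density measured in these mammograms will be used in the analyses of the ITT population". Women with no further mammogram are assumed to have no reduction.

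**The concern.** A yes/no rule with two possible readings can give a go at one visit and a no-go at the other, and the text offers no tie-break. If the visit were chosen after the data were seen, an inert product would pass more often than the 50% in Table 5. The simulations do not settle the matter. They use mammograms about two years apart, and Tables 4 and 5 score a single value. The density tool is also slightly open: 7.3 uses both Volpara and Stratus, although 5.5 and 9.1.3 point to Stratus.

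The second worry is the estimate itself. A sign rule that passes an inert product half the time carries little information, so the next trial must be sized from the effect size and its uncertainty. The text names only the former.

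**Working it through.** **Inputs.** Arms of 30, so 60 v 30 for mt-mc. Table 5, first column, for thresholds >0, >1, >2 and >3: 50, 24, 8 and 2%. Table 4, 12% column: 7, 20, 43 and 66%. Table 1 (oral tamoxifen, n = 32, no placebo): baseline 17.6, change -1.8 at 3 months and -2.3 at 6 months. Table 5 is headed 10/12/14%, but its caption says null and 9.1.3 lists 0/1/2% as the null cases. I read the first column as 0%.

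**1. The plan's own figure.** With no true effect mt-mc is centred on zero, so P(mt-mc > 0) = 0.50 by symmetry at any SD. This matches Table 5 and holds at 3 months and at 6 months alike.

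**2. Standard error implied by the tables** (normal approximation; fits, not independent reproductions).

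- Table 5, first column: 1/z(0.76) = 1.42, 2/z(0.92) = 1.42, 3/z(0.98) = 1.46. SE 1.425 returns 50.0, 24.1, 8.0 and 1.8%.
- Table 4, 12% column: mean 2.32 with SE 1.59 returns 7.3, 20.4, 42.1 and 66.6%.
- Fitting all six columns gives SEs of about 1.43 to 1.73 percentage points.

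**3. Two visits, no effect.** With correlation ρ between visits (an assumption; the documents give none), P(both positive) = 1/4 + asin(ρ)/(2π), and P(either positive) = 1 - P(both).

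| ρ | one named visit | either visit suffices | both required | signs disagree |
|---|---|---|---|---|
| 0.9 | 50% | 57% | 43% | 14% |
| 0.7 | 50% | 63% | 37% | 25% |
| 0.5 | 50% | 67% | 33% | 33% |

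The plan states neither combination rule, and they move the rate in opposite directions.

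**4. Does the visit change the false-negative rate?** From Table 1, 1.8/17.6 = 10.2% and 2.3/17.6 = 13.1%. Linear interpolation on the >0% row of Table 4 (10, 7 and 3% at 10, 12 and 14%) gives 9.7% and 4.9%. This puts uncontrolled changes on an oral drug into a table of assumed treatment-induced reductions. It is an illustration, not an error rate by visit.

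**5. Precision and next-trial size.** SD = SE/√(1/60 + 1/30); half-width = 1.96 × SE; n per arm = 2(1.96 + 0.842)² SD²/d², with two-sided 5% and an assumed 80% power. The formula compares means; 9.1.3 foresees a Wilcoxon test.

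| SE | SD | d | 95% CI for mt-mc | n per arm |
|---|---|---|---|---|
| 1.425 | 6.37 | 2.29 | -0.5 to 5.1 | 122 |
| 1.594 | 7.13 | 2.318 | -0.8 to 5.4 | 149 |
| 1.73 | 7.74 | 2.318 | -1.1 to 5.7 | 175 |

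For one dose against placebo (30 v 30) the half-width is 1.96 × SD × √(2/30), or 3.2 to 3.9 points.

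**6. Is anything uncomputable?** The intervals need only the n, mean and SD of change in each arm. Those statistics are the ones 9.1.1 lists, though under a baseline heading, and 9.1.2 undertakes to summarise the differences quantitatively at both visits.

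**The case for a change.** The best case for a change is that the protocol, not the SAP, sets the decision rule, so the rule should be readable there. Six months can be inferred from the treatment period in 5.6, but nothing states it for mt-mc. Naming the visit would cost one line and close off a choice made after the data are seen. For a pilot whose product is an effect size, an interval is part of that product. The spread is wide: at SE 1.59, one SE either side of 2.3 points moves the next trial from about 150 women per arm to about 52 or about 1,575.

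The omission itself stands, and stating the visit and an interval in the SAP would be good practice. The harm claimed for it does not follow. The false-go rate above 50% needs an either-visit or after-the-fact choice that the plan nowhere permits, and the SAP is due before database lock. A false go leads to a larger, adequately powered trial, and the 50% risk is printed openly. Reporting both visits also has a purpose, since study length is among the decisions the pilot informs. The wide range of sizes comes from having 90 women; prespecifying an interval does not narrow it.

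A fuller rewrite could also do harm. Treating every exit mammogram as a 6-month value would be a carry-forward rule: 10.6 seeks exit images from women who stop after as little as a week.

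**Conclusion.** No change follows. This is missing detail that analysts fill sensibly: mt-mc on Stratus density at 6 months, the end of the treatment period, with the 3-month result beside it and each difference given with its SD or interval. No stated rule or figure is shown to be wrong. The false-go rate is 50% at any single visit. It is 57 to 67%, or 43 to 33%, only under combination rules the plan does not state and for assumed correlations of 0.9 to 0.5. The expected interval of about ±2.8 to 3.4 points around 2.3 includes zero, and the next trial would need roughly 120 to 175 women per arm at that estimate.

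These figures assume normality, SEs fitted to Tables 4 and 5 (built on roughly two-year change in women aged 40 to 74), the first column of Table 5 read as the 0% null, and 80% power. The judgement that no change is needed does not depend on them. It rests on the deferral to a SAP approved before lock, the planned reporting of both visits, and the declared exploratory purpose. The SAP's text was not available, so it may already settle both points.

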9.1.4 Analysis of the secondary outcome

Estimate dose dependent differences in compliance, side effects and local tolerability and laboratory results.

9.1.5 Analysis of the tertiary outcome

Estimate if plasma level concentrations of endoxifen are related to primary and secondary endpoints.

9.1.6 Interim analysis

No interim analyses will be performed.

10 INVESTIGATIONAL PLAN

10.1 The Karma Study Centre

Women participating in the Karma CREME-1 study will conduct all study specific activities, except the mammography, at the Karma Study Centre. The Karma Study Centre is located in the facilities of Södersjukhuset Breast Centre (SöS Bröstcentrum) at Södra station, where mammographic examinations are conducted, and is daily staffed with two full time employed nurses and one full time employed investigator

10.2 Selection of study population

Eligible women will be identified from those women invited for mammography screening at SöS Bröstcentrum.

The rationale to exclude women with the lowest density is based on experience from the Karma Group previous study of mammographic density reduction in patients on tamoxifen. In that study the researchers had to exclude women with the lowest density since density change was not possible to measure in women with very low density. The lower cut off for inclusion is set to 4.5% density, measured by Volpara. The 4.5% level corresponds to the clinically used BI-RADS score A.

The rationale to exclude premenopausal women is to avoid natural fluctuations of mammographic density related to the changing hormone levels associated with the menstrual cycle.

10.3 Inclusion criteria

To participate, the women must meet the following inclusion criteria:

- Attending the national mammography screening program, i.e., aged 40-74 and have performed a screening mammogram maximum 3 months prior to study inclusion
- Mammographic density $\geq 4.5\%$ density (volumetric) measured by Volpara, at the screening mammogram performed in connection to baseline (maximum 3 months prior to inclusion). The threshold value of 4.5% corresponds to the clinically used BI-RADS score A
- Postmenopausal, defined as no period of menstruation during last 12 months independent of any hormonal treatment
- Informed consent must be signed before any study specific assessments are performed

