6 BENEFIT-HARM ASSESSMENT

6.1 Background

In a broader sense, ethical considerations in clinical trials should focus on answering the question – does knowledge generated through the trial outweigh the possible harms inflicted on the participants? The most important task is to take the safety of study participants into consideration. Breast cancer incidence has increased rapidly over the last generations and currently one women per minute is diagnosed with breast cancer in Europe. It could therefore be argued that efforts taken to reduce the number of breast cancers are much needed. Tamoxifen has been used for adjuvant therapy for breast cancer for several decades and the side effects of tamoxifen are well-known. Side effects range from menopausal symptoms and mood swings to increased risks of endometrial cancer and thromboembolism. Tamoxifen has also been found to reduce the number of newly diagnosed cancers in perfectly healthy women but is not used to any larger extent due to the risk of bothersome as well as potentially very serious side-effects. Little is known about the side effects of endoxifen. Therefore, a conservative approach must be to assume that the toxicity of endoxifen is identical to that of

tamoxifen and that there is a dose dependency is used. The following sections discuss the potential risks associated with exposing healthy volunteers to topical endoxifen and the associated mitigation strategies. Possible benefits of participating in the trial are also described, as well as benefit-harm assessment of frequent mammograms.

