6.2 Safety

The most serious side effects of tamoxifen are thromboembolic events, endometrial cancer, sarcoma of the uterus and liver damage such as cirrhosis and steatosis. Markers of the coagulation system, liver function and levels of sex hormone binding globulin (SHBG) were therefore tested in the phase I topical endoxifen trial. Comparing levels before trial initiation and at 28 days of exposure to the study drug revealed no influence on these parameters, not even in the highest dose (10 mg) category. For more detailed information on the phase 1 results, please see Investigator Brochure.

During pregnancy, tamoxifen and its metabolites interact with rapidly growing and developing embryonic or foetal tissues. Tamoxifen exposure during pregnancy could lead to congenital malformations, spontaneous abortions and even foetal deaths.

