6.2.1 Risk mitigation strategy -Safety

The phase 1 data does not indicate a systemic influence on the systems but since it cannot entirely be ruled out that there is an effect on the coagulation system, liver function or SHBG, markers of their function will be measured at 3 and 6 months in this phase 2 study.

Patients with a previous cardiovascular event will be excluded from the study. Blood pressure will be measured before entering the study and women with a blood pressure $>140/90$ mm Hg will not be included in the trial. Possible signs of vaginal bleeding will be addressed immediately. Since only postmenopausal women will be included, pregnancy related safety issues are not a concern.

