10.4 Exclusion criteria

To participate, the women must not meet any of the exclusion criteria listed below at entry of the study nor under time of treatment.

[figure not shown]
Criteria related to study design

- Any previous or current diagnosis of breast cancer (including carcinoma *in situ*).
- Any previous diagnosis of cancer with the exception of non-melanoma skin cancer and *in situ* cancer of the cervix.
- A history of major surgery of the breast, e.g., reduction or enlargement, which might affect density measurements.
- Mammographic BI-RADS *malignancy* code 3, or above, at baseline mammography, or at mammography during time of treatment. Recall for additional examinations due to technical problems with the mammogram is accepted.
- Currently using estrogen and progesterone based hormone replacement therapy (oral or patches). Local estrogen treatment is accepted (ex. Vagifem).
- Non-medical approved drugs against hot-flashes including phytoestrogen.

Criteria related to safety

- A history of thromboembolic disease such as embolus, deep vein thrombosis, stroke, TIA or myocardial infarction.
- Known APC (Activated Protein C)-resistance, an inherited haemostatic disorder.
- Women who have an increased risk of venous thrombosis due to immobilization, e.g., using wheelchair.
- Known uncontrolled diabetes.
- Hypertension at baseline, defined as systolic pressure higher than 140 mm Hg and diastolic higher than 90 mm Hg
- Prescribed and regular use of anticoagulants (defined as substances included in group B01A in the ATC-system)
- Not able to understand the study information and/or informed consent.

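### The definition of postmenopausal in 10.3 has two readings, and only one of them supports the dismissal of pregnancy risk in 6.2.1 and the density rationale in 5.5 and 10.2

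*Combined protocol and SAP*

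**What the plan says.** Two inclusion criteria in 10.3 matter here. Age follows the screening programme: "Attending the national mammography screening program, i.e., aged 40-74". Menopausal status is "Postmenopausal, defined as no period of menstruation during last 12 months independent of any hormonal treatment". No hormone level or cause of the amenorrhoea is asked for.

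The hormone-related exclusion in 10.4 reads "Currently using estrogen and progesterone based hormone replacement therapy (oral or patches"; local estrogen is accepted. Section 10.7.10 prohibits the same class of replacement therapy unless local, without limiting it to tablets and patches. Both sections also bar unapproved hot-flush remedies, including phytoestrogens.

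On safety, 6.1 takes the position "Therefore, a conservative approach must be to assume that the toxicity of endoxifen is identical to that of" tamoxifen, and 6.2 states "Tamoxifen exposure during pregnancy could lead to congenital malformations, spontaneous abortions and even foetal deaths". Section 6.2.1 then closes the matter: "Since only postmenopausal women will be included, pregnancy related safety issues are not a concern".

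On measurement, 10.2 explains: "The rationale to exclude premenopausal women is to avoid natural fluctuations of mammographic density related to the changing hormone levels". Section 5.5 gives the same reason, and treats freedom from cycle-related change as following by definition from being postmenopausal.

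**The concern.** The safety argument and the measurement argument both rest on one line of the eligibility criteria, and that line does not have a single meaning. On one reading, a woman in her forties whose periods are suppressed by a hormonal product, but whose ovaries still function, meets the criterion. If she stopped that product during the 6 months of treatment she could become fertile while on study drug, a situation that 6.2.1 treats as impossible. Two investigators could also decide the same woman's eligibility differently, each in good faith.

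For the primary endpoint, such women could bring back some of the hormonal variation in density that the restriction is meant to remove.

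**Working it through.** No formula applies and the plan gives no figure to reproduce. The check is to follow each reading through the sections that depend on it.

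**1. The two readings of 10.3.**

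| | Reading A: regardless of hormonal treatment | Reading B: not caused by hormonal treatment |
|---|---|---|
| Amenorrhoea under a hormonal contraceptive or intrauterine device | Counts as menopause | Does not count |
| Premise of 6.2.1 (all participants postmenopausal) | Not secured | Supported |
| Premise of 5.5 and 10.2 (no cycle-related density change) | Not secured | Supported |

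Nothing elsewhere in the documents says which reading is meant.

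**2. Does another criterion close the gap under Reading A?** Sections 10.4 and 10.7.10 restrict estrogen-and-progesterone replacement therapy and unapproved hot-flush products. Neither names contraceptives, hormonal intrauterine devices or progestogen-only products. The replacement-therapy rules narrow the gap but do not close it.

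**3. Is there a check behind the definition?** Pregnancy is not among the exclusions in 10.4. Appendix A lists no pregnancy test and no assessment of menopausal status. Section 10.5.3 mentions sex hormones among the baseline blood tests, but that blood is drawn after randomisation, and the only hormone-related test in the Appendix A safety panel is SHBG. It cannot serve as an eligibility check.

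**4. Would a change during treatment trigger anything specific?** Section 10.4 applies the exclusion criteria during treatment as well as at entry, and 10.6 makes meeting one a reason for withdrawal. Menopausal status is an inclusion criterion and pregnancy is not an exclusion, so neither enters that rule. Only general grounds remain, such as other medical reasons.

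**5. What routine reporting exists?** Concomitant therapy is recorded (10.7.9). Vaginal bleeding of at least the middle intensity grade is an adverse event of interest (11.4.1), and abnormal bleeding is to be investigated promptly (11.4.1.1). Questionnaires are due at months 1, 3 and 6. These routes could bring a change of hormonal product or a return of bleeding to light, but none is designed to detect fertility or pregnancy.

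**6. Which ages are in play?** Section 9 says only Karma Cohort members will be invited, and 5.1 dates that cohort to 2010-2013. If members were at least 40 when they joined (an assumption; 5.1 gives no ages), the youngest at enrolment in 2018 would be about 40 + (2018 − 2013) = 45, or 44 allowing for months. Sections 10.2 and 10.5.1, however, describe invitation of screening attendees generally, and 10.3 sets the floor at 40. Women in their early forties may therefore be few or absent. The argument applies equally to the later forties.

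**7. Size.** The documents give no proportion of attendees with hormone-induced amenorrhoea. Foetal exposure would further require that the woman be premenopausal, stop the method within 6 months, conceive, and be among the 60 of 90 allocated to active drug. None of the first three steps has a figure in the documents, so no count is offered.

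**The case against.** The best counter-argument is that the surrounding text favours Reading B. The criterion opens by requiring postmenopausal status, the synopsis describes the participants as postmenopausal, and 10.2 states the intention to exclude premenopausal women. On that reading the definition already does its job. This has weight: a reader might infer from Reading A that the protocol admits fertile women, and the documents do not establish that. They establish wording that permits it, against a stated intention that does not. The intention is not itself a criterion, so the need to clarify remains.

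A reader might also infer that a return of fertility would pass unnoticed. That goes too far, given the reporting of bleeding and concomitant therapy and the scheduled contacts. What stands is that none of these is a check for pregnancy.

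Third, some eligibility material is not visible: the screening form, the baseline questionnaire and other study-file documents, and a figure in 10.4. A menopausal-history question may exist there. The absences noted here hold only for the protocol text available.

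Finally, a reader might take this as a threat to the validity of the density comparison. The trial is randomised, double-blind and placebo-controlled, and density measurement is also blinded, so a few such women would add variability without favouring an arm. The documents do not allow the effect on the difference in mean density reduction to be quantified.

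**Conclusion.** The point holds as an ambiguity with a safety consequence. Section 10.3 can be read so that it does not ensure menopause, the visible exclusions do not compensate, and 6.2.1 dismisses a hazard recognised in 6.2 on the strength of that definition alone. Sections 5.5 and 10.2 lean on the same line. It should be fixed, because the harm is one the protocol itself describes as grave and the correction is almost free. It is not shown to be a critical defect: the protective reading is available, the number of women affected is unknown, and the consequence for the primary endpoint is noise. The conclusion assumes that the study-file material does not already settle the definition.

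**What to change.** Reconcile 10.3 with 6.2.1, 5.5 and 10.2. Reword the definition so that it has one meaning and supports the postmenopausal status those sections assume. One possibility is to state that the amenorrhoea is not attributable to hormonal treatment or contraception; the exact criterion is for the sponsor and clinicians to set. Record current use of any hormonal product at pre-screening (10.5.2), so that eligibility can be judged before randomisation. If the broader reading is what the sponsor intends, leave the scope of 10.3 as it is, make that reading explicit, and revise the statement in 6.2.1, which would then no longer follow; the rationale in 5.5 and 10.2 would need the same review.

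The cost is one line of text and one history question, with no added test or visit. The downside of the narrower definition is that a few truly postmenopausal women using a hormonal device may be turned away.
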